3.9.8. Ocular Toxicity and Stopping Criteria

All subjects will be advised to use prednisolone phosphate 1% or dexamethasone 0.1% eye drop 4 times a day (QID) for 4 days starting 1 day prior to each dose. Additional use of lubrication eye drops (artificial tears) QID PRN throughout the trial is recommended, especially if subject develops any ocular symptoms. Subjects who develop Grade 3 ocular or corneal toxicity will be allowed to continue study treatment after resolution to \leq Grade 1; each case will be discussed individually between the investigator and the Medical Monitor. Subjects who develop \geq Grade 4 ocular or corneal toxicity will be permanently removed from study. Refer to Section 3.10.2 for further guidance.

3.10. Guidelines for Events of Special Interest and Dose Modifications

3.10.1. Guidelines for Events of Special Interest

The severity of adverse events (AEs) will be graded utilizing the National Cancer Institute- Common Toxicity Criteria for Adverse Events (NCI-CTCAE), version 4. Guidelines for dose modifications and interruptions for management of common toxicities associated with the study treatment are provided in this section.

3.10.2. Predicted Toxicities and Proposed Dose Adjustments/Stopping Criteria

Toxicity	Grade/symptoms	Recommendations
Creatinine elevation which cannot be explained by concomitant sepsis, other severe infection with fever or dehydration	If absolute serum creatinine increase from baseline of > 0.3 mg/dL (26 µmol/L) but ≤ 0.5 mg/dL (44 µmol/L)	Repeat within 48 hours 
 If creatinine returns to ≤ 0.3 mg/dL (26 µmol/L) above baseline 
 Continue GSK2857916 at current dose If creatinine remains elevated: > 0.3 mg/dL (26 µmol/L) but ≤ 0.5 mg/dL (44 µmol/L) from baseline 
 Continue GSK2857916 Monitor creatinine at least weekly Consider 25% dose reduction if creatinine remains elevated (after discussion with Medical Monitor)
	If absolute serum creatinine increase from baseline of > 0.5 mg/dL	Repeat within 48 hours: 
 If confirmed: withhold therapy, institute treatment and monitoring as clinically indicated, and follow for resolution Discuss any further dosing with Medical Monitor* 
* Medical Monitor should consult GSK's nephrotoxicity panel about plans to continue therapy

Serum creatinine ≥ Grade 3	>3.0mg/dL from baseline or 3.0-6.0xULN	
 Provide appropriate medical treatment. Permanently discontinue treatment with GSK2857916

Toxicity	Grade/symptoms	Recommendations
Albuminuria	>2000mg/24 hr	
 • Re-test (at least 7 days apart). 
 ○ If not confirmed, continue GSK2857916 at 100% dose ○ If confirmed on re-test and no clear evidence of disease progression* 
 ▪ Interrupt treatment with GSK2857916 ▪ Repeat testing within 4 weeks 
 • If albuminuria \leq2000mg/24hr may restart GSK2857916 with 25% dose reduction • If albuminuria remains >2000mg/24hr after 4 weeks; Permanently discontinue GSK2857916 and withdraw subject from study; provide treatment as clinically indicated and follow for resolution 
* Medical Monitor should consult GSK's nephrotoxicity panel about plans to continue therapy

Thrombocytopenia	Grade 3: >25 and <50x10 ⁹ /L	
 • Where estimated blood loss is \geq 10 mL: withhold the treatment: • No bleeding: continue treatment with 25% dose reduction
	Grade 4: \leq 25x10 ⁹ /L	
 • Withhold the dose. Consider restarting with 25% dose reduction if recovered to >25x 10⁹/L , only if there is no active bleeding at time of treatment re-start • If thrombocytopenia is considered disease related, is not accompanied by bleeding, and recovers with transfusion to >30 x10⁹/L within 14 days, restarting treatment at 50% dose reduction may be considered after discussion with the GSK Medical Monitor
Febrile neutropenia	>38.3°C for > 1 hr AND ANC < 1000/mm ³	
 • Withhold GSK2857916, implement treatment with antibiotics, antivirals and antifungals, as clinically indicated, • If resolved \leq 14 days, may restart GSK2857916 treatment at 25% dose reduction

Toxicity	Grade/symptoms	Recommendations
INR prolongation	> 1.5	
 • Evaluate liver function and other possible causes for INR elevation (use of anticoagulants, work up for DIC and provide treatment as clinically indicated 
 – If subject meets liver stopping criteria: Withdraw from study treatment as per liver stopping criteria – If subject has evidence of DIC: withdraw subject from study treatment – If isolated INR elevation and subject does not meet liver stopping criteria 
 • Withhold the dose and re-test INR within 48hrs • Discuss the case with Medical Monitor and consider 25% dose reduction
	> 2.0	
 • Evaluate possible reasons as above, treat adequately if underlying condition has been identified • Restart treatment with GSK2857916 at 25-50% dose reduction if toxicity resolved to ≤ 1.5 baseline and after discussing the case with GSK Medical Monitor
	>2.5	
 • Evaluate and provide medical treatment if necessary • If INR prolongation is not related to use of anticoagulants withdraw subject from study treatment
Ocular/corneal toxicity	Grade 1	
 • Continue treatment with current dose of GSK2857916. • Consult ophthalmologist within 7 days
	Grade 2	
 • First occurrence: 
 ○ Interrupt treatment with GSK2857916 ○ Consult ophthalmologist immediately ○ When recovered to $G \leq 1$ Restart treatment with GSK2857916 at 25% dose reduction upon resolution to $\leq G1$ • Second occurrence: 
 ○ Interrupt treatment with GSK2857916 ○ Consult ophthalmologist immediately ○ Once resolved to $\leq G1$ or less: Restart treatment with GSK2857916

Toxicity	Grade/symptoms	Recommendations
		
at additional 25% dose reduction
 
 • Third occurrence: 
 ○ Further treatment with GSK2857916 only allowed after discussion and in agreement with medical monitor
	Grade 3	
 • First occurrence 
 ○ Consult ophthalmologist immediately ○ Interrupt treatment with GSK2857916 ○ Once resolved to \leq G1: Restart treatment with GSK2857916 at 25% -50% dose reduction if the investigator and Medical Monitor agree that the potential benefits outweigh the risks • Second occurrence 
 ○ Consult ophthalmologist immediately ○ Permanently discontinue treatment with GSK2857916
	Grade 4	
 • Consult ophthalmologist immediately • Permanently discontinue treatment with GSK2857916
Pneumonitis	Grade 1	
Withhold dose and follow recommendations below: Obtain high resolution chest CT if possible.
 
 • CT scan (high-resolution with lung windows) recommended • Clinical evaluation and laboratory work-up for infection • Monitoring of oxygenation via pulse-oximetry recommended • Consultation with pulmonologist recommended • If resolved: Retreatment at the full dose is possible
	Grade 2	
Withhold treatment with GSK2857916
 
Follow recommendations below: Obtain high resolution chest CT if possible.
 
 • CT scan (high-resolution with lung windows) • Clinical evaluation and laboratory work-up for infection • Consult pulmonologist

Toxicity	Grade/symptoms	Recommendations
		
 • Pulmonary function tests (PFT) – if abnormal, repeat every 8 weeks until back to baseline • Bronchoscopy with biopsy and/or bronchoalveolar lavage (BAL) recommended • Symptomatic therapy including corticosteroids if clinically indicated If resolved: Restart treatment with 50% dose reduction
	Grade 3/Grade 4	Permanently discontinue treatment with GSK2857916, and follow recommendations below. 
 • Obtain CT scan (high-resolution with lung windows) • Clinical evaluation and laboratory work-up for infection • Consult pulmonologist • PFT – if abnormal, repeat every 8 weeks until back to baseline Bronchoscopy with biopsy and/or BAL if possible • Symptomatic therapy including corticosteroids as clinically indicated

3.10.3. Dose Modifications

For GSK2857916 toxicities not specifically addressed in the protocol follow the guidelines outlined in [Table 13](#).

Table 13 Dose Adjustment/Stopping Criteria

Toxicity Grade ^a	Dose Modification of GSK2857916
Grade 1	
 Continue at current dose level. Consider supportive care recommendations
Grade 2	
 If toxicity is considered not clinically relevant, continue with 100% scheduled dose If toxicity is considered clinically relevant withhold the dose until toxicity resolves to Grade 1 or baseline. If resolved within 14 days, then restart at current dose level. Consider supportive care recommendations If not resolved within 14 days, discuss with GSK Medical Monitor
Grade 3	
 Withhold dose until toxicity resolves to Grade 1 or baseline, unless condition fits exceptions noted below. If resolved within 14 days, resume treatment at dose reduced by 25% (first dose reduction), or 50% (second dose reduction). Consider supportive care recommendations. If toxicity is resolved within period longer than 14 days, continuation of treatment may be considered on an individual basis if benefit to subject can be demonstrated and if the investigator and medical monitor agree that for a given subject the benefits may outweigh the risks 
Exceptions:
 
 Subjects who develop G3 toxicities which respond to standard treatment and resolve to ≤G1 within 48 hours may continue treatment at scheduled or reduced dose Permanently discontinue for grade 3 or greater QTc prolongation i.e., QTcF >500 msec or QTcF increase by > 60 msec from baseline Troponin elevations: See Section 3.9.3 for troponin stopping criteria
Grade 4	
 Permanently discontinue study medication 
Exceptions:
 
 G4 thrombocytopenia with no sign of bleeding, if recovered within 14 days. For dose reductions see Section 3.10 G4 lymphopenia (dose reductions by 25-50% may be considered)

a. Possibly related to investigational drug.

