3.3.3. Dose-Limiting Toxicity - Part 1 only

Any subject in Part 1 (Dose Escalation) who received at least one dose of the drug (regardless of schedule) will be evaluated for DLTs. Safety data together with DLTs will be reviewed during the dose escalation meetings prior to opening enrollment into subsequent cohorts (see Section 12.1).

Subjects who have been withdrawn from the study for reasons other than toxicity but prior to completion of DLT observation period will be replaced. An event will be considered a DLT if its relationship to the investigational agent cannot be ruled out occurs within the DLT reporting period (first 21 days of treatment for schedule 1, and first 28 days for schedule 2) and meets one of the following criteria:

- Albuminuria ≥ 2000 mg/24 hr which has been confirmed by repeat test at least 7 days apart and is not considered to be related to disease progression based on consultation of investigator with GSK medical monitor
- Grade 4 neutropenia (without fever) lasting ≥ 7 days
- Febrile neutropenia lasting ≥ 72 hours
- Grade ≥ 3 thrombocytopenia associated with bleeding where estimated blood loss is > 10 mL or Grade 4 thrombocytopenia lasting > 7 days and not responding to platelet transfusions
- Any Grade 3 or greater non-hematologic toxicity as described in Common National Cancer Institute-Terminology Criteria for Adverse Events (NCI-CTCAE) version 4.0 [NCI, 2009] with the exception of the following Grade 3 events that can be controlled within 48 hours with routine supportive measures
 - Nausea and vomiting that can be controlled with anti-emetics
 - Diarrhea that can be controlled with anti-diarrheals
 - Rash or other skin reactions that can be controlled with antihistamines and steroids
 - Clinically asymptomatic electrolyte abnormalities which can be corrected within 48 hours)
- Liver toxicity meeting pre-specified GSK liver stopping criteria (see Liver in Section 3.9.1)

Tumor lysis syndrome does NOT constitute a DLT (Section 3.9.7).

A subject who develops a DLT will be allowed to stay on study only if the toxicity did not meet stopping criteria and recovered to \leq Grade 1 within 14 days, or after a longer recovery time if benefit to subject can be demonstrated and if the investigator and medical monitor agree that for a given subject the benefits may outweigh the risks.

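### For drug-related Grade 4 thrombocytopenia, Section 3.10.2 lets restart be considered in cases where Table 13 requires permanent discontinuation

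*Protocol*

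**What the plan says.** **Section 3.10.2, thrombocytopenia.** Grade 4 is a platelet count of 25×10⁹/L or below, and the entry has two bullets.

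- The first reads "Withhold the dose. Consider restarting with 25% dose reduction if recovered to" a count above 25×10⁹/L, and "only if there is no active bleeding at time of treatment re-start". It has no time limit.
- The second covers thrombocytopenia considered disease related. Restart may be considered, after discussion with the Medical Monitor, if the event "is not accompanied by bleeding, and recovers with transfusion to" a count above 30×10⁹/L within 14 days.

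**Section 3.10.3, Table 13.** The lead-in says: "For GSK2857916 toxicities not specifically addressed in the protocol follow the guidelines outlined in" the table. A footnote restricts the table to toxicity possibly related to the investigational drug. The Grade 4 default is "Permanently discontinue study medication". One listed exception is "G4 thrombocytopenia with no sign of bleeding, if recovered within 14 days", followed by "For dose reductions see Section" 3.10.

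**Section 6.3.** Treatment may be permanently discontinued for a dose delay of more than 14 days, unless the investigator or Medical Monitor agree that the subject benefits.

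**Section 3.3.3 (Part 1 only).** "A subject who develops a DLT will be allowed to stay on study only if the toxicity did not meet stopping criteria" and, in addition, it recovered to Grade 1 or less within 14 days, or later if benefit can be shown and the investigator and Medical Monitor agree.

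**The concern.** Section 3.10.2 and Table 13 address the same event with different conditions for going back on treatment. They differ on when bleeding counts (at restart, or with the event) and on whether there is a deadline. Two sites that each follow the protocol could re-treat one subject and permanently stop another with an identical course.

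Section 3.1 allows no waivers or exemptions, so sites need a single readable instruction. Section 13.7.2.2 lists hematologic toxicities, thrombocytopenia among them, as adverse events of clinical interest whose characteristics, including action taken, are summarised separately. The action taken would then partly reflect which section a site followed.

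**Working it through.** There is no figure to reproduce, so the check compares the text of the two rules.

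**Step 1. Fix the population.** Table 13 covers only toxicity possibly related to study drug. The matching rule in Section 3.10.2 is its first Grade 4 bullet. The second bullet is for disease-related cases and carries both a no-bleeding condition and a 14-day limit of its own.

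**Step 2. Compare the conditions.**

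| Condition | Section 3.10.2, first Grade 4 bullet | Table 13, Grade 4 exception |
|---|---|---|
| Bleeding | None active when treatment restarts | None with the event |
| Time limit | None stated | 14 days |
| Recovery count | Above 25×10⁹/L | Recovery required, count not stated |
| If not met | Dose stays withheld | Permanent discontinuation |

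**Step 3. Apply both rules.** Take a subject whose platelets are now above 25×10⁹/L and who is not bleeding at restart.

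| Bleeding during the event | Recovery | Section 3.10.2 | Table 13 | Agree? |
|---|---|---|---|---|
| No | Within 14 days | Restart may be considered | Exempt from discontinuation | Yes |
| No | After 14 days | Restart may be considered | Permanent discontinuation | No |
| Yes, since stopped | Within 14 days | Restart may be considered | Permanent discontinuation | No |
| Yes, since stopped | After 14 days | Restart may be considered | Permanent discontinuation | No |

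The sections agree in one of the four combinations. These are types of case, not proportions of subjects.

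**Step 4. Look for a text that decides between them.**

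- The lead-in to Table 13 would make it a residual rule. But the table then names Grade 4 thrombocytopenia, sets two conditions for it, and points to Section 3.10 for dose reductions only. If Section 3.10.2 alone governed restart, those conditions would have no function.
- Section 6.3 makes discontinuation after a delay of more than 14 days discretionary. Table 13's Grade 4 exception has no benefit override, although its Grade 3 row does. Section 6.3 does not mention bleeding.
- Section 3.3.3 makes staying on study depend on whether stopping criteria were met. For this toxicity, that depends on which section is read.

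**The case against.** The best counter-argument is the lead-in to Table 13. Thrombocytopenia has its own Grade 3 and Grade 4 entries in Section 3.10.2, so on its face that section governs and the Table 13 entry is a leftover. Section 3.10.2 also offers recommendations and only asks that restart be considered. A cautious site could satisfy both texts by restarting only when Table 13's conditions are met as well. Late restart is not wholly uncontrolled either, because Section 6.3 calls for a judgement of benefit.

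Much of this stands. It shows that Section 3.10.2 permits restart and does not direct it, and that the lead-in leans towards that section. It does not remove the conflict: permission to restart is still incompatible with mandatory discontinuation, and nothing tells a site to apply the stricter text.

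A reader might infer more than the documents support:

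- **That every Grade 4 case with bleeding or late recovery is affected.** Disease-related cases fall under the second bullet, which has both conditions, and Table 13 does not reach events unrelated to study drug.
- **That Table 13 sets Grade 1 or baseline as the Grade 4 recovery target.** That target stands in its Grade 2 and Grade 3 rows. The Grade 4 exception gives no count.
- **That Section 3.3.3 is a third competing rule.** It is an added condition for Part 1 dose-limiting toxicities only and can operate on top of Section 3.10.2.
- **That the maximum tolerated dose or the response rate is compromised.** Nothing in the protocol shows this.

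**Conclusion.** The conflict is real and narrow. For Grade 4 thrombocytopenia possibly related to study drug, a subject who bled but has stopped, or who recovers after 14 days, may be restarted under Section 3.10.2 and must be permanently discontinued under Table 13.

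The bleeding half assumes that Table 13's no-bleeding condition describes the event and not only the moment of restart, which is its natural reading. The time-limit half does not depend on that assumption.

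The number of subjects affected cannot be estimated from the protocol. The consequence is inconsistent handling of individual subjects, and less interpretable records of action taken and treatment discontinuation for this toxicity. It should be corrected. No view is taken on which rule is clinically right.

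**What to change.** Reconcile the Grade 4 thrombocytopenia entries in Section 3.10.2 and Table 13 into one rule that states:

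- whether bleeding is judged over the event or at restart;
- whether there is a time limit;
- what platelet count constitutes recovery.

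Alternatively, state which section governs and remove the other set of restart conditions. In either case, say how the Section 3.3.3 condition for Part 1 dose-limiting toxicities applies alongside the rule. The sponsor chooses the clinical content.

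The cost is amendment wording in two tables and one clarifying sentence for Section 3.3.3. Sample size and planned analyses are unaffected.

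### Table 13 handles possibly drug-related Grade 4 lymphopenia less strictly than Grade 3: it states no hold or recovery condition, and the dose reduction is optional

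*Protocol*

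**What the plan says.** Section 3.10.3 gives Table 13 its scope: for "toxicities not specifically addressed in the protocol follow the guidelines outlined in" that table. A footnote limits it to events possibly related to the drug. Section 3.10.2 has rows for creatinine, albuminuria, thrombocytopenia, febrile neutropenia, INR, ocular toxicity and pneumonitis, but none for lymphopenia.

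For Grade 3, Table 13 says: "Withhold dose until toxicity resolves to Grade 1 or baseline, unless condition fits exceptions noted below". On restart: "If resolved within 14 days, resume treatment at dose reduced by 25% (first dose reduction), or 50% (second dose reduction". Two provisions soften this. Events that respond to standard treatment and fall to Grade 1 or less "within 48 hours may continue treatment at scheduled or reduced dose". Where recovery takes more than 14 days, continuation is possible if benefit can be shown and the investigator and medical monitor agree. No Grade 3 exception names lymphopenia.

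For Grade 4 the default is permanent discontinuation, with two exceptions. One is "G4 thrombocytopenia with no sign of bleeding, if recovered within 14 days". The other is "G4 lymphopenia (dose reductions by 25-50% may be considered".

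**The concern.** A graded dose-modification table should not become more permissive as severity rises. At Grade 3 the hold, the recovery target and the reduction are written as instructions. At Grade 4, lymphopenia is released from the discontinuation rule and nothing firm replaces it: no hold, recovery grade, time limit or discussion with the medical monitor. The reduction is only something that may be considered.

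At stake is consistency between sites on a safety action. Faced with a first Grade 4 result on a dosing day, one site may hold by analogy with Grade 3 while another gives the full dose, and both would be within the text. Section 1.3.1 names immunosuppression as a risk, so the dosing action should be clear.

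**Working it through.** There is no planned figure to reproduce. The check compares the texts and counts visits.

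**Step 1: the two grades side by side (section 3.10.3, Table 13).**

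| Element | Grade 3 lymphopenia | Grade 4 lymphopenia |
|---|---|---|
| Permanent discontinuation | not required | waived |
| Hold | directed | not stated |
| Recovery before restart | Grade 1 or baseline | not stated |
| Reduction on restart | directed: 25%, then 50% | optional: 25-50% |
| Relief | resolved to Grade 1 or less within 48 hours | none needed, as no hold is stated |
| Recovery beyond 14 days | shown benefit plus investigator and monitor agreement | not stated |

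Except for the waived discontinuation, every element that binds at Grade 3 is absent or optional at Grade 4.

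**Step 2: does another section supply the missing rule?**

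- Section 1.3.1 provides for following lymphocytes and immunoglobulins and treating infections. It gives no dosing rule for lymphopenia.
- Section 3.3.3 does not list lymphopenia among the dose-limiting toxicities, and its Grade 3-or-higher catch-all is confined to non-hematologic events. Its recovery rule for subjects with such a toxicity therefore does not apply.
- Sections 3.10.1 and 3.10.2 contain no lymphopenia rule.
- Section 4.4 caps reductions at two per subject. It adds no hold.
- Section 6.3 allows stopping at the investigator's discretion and addresses delays over 14 days. It does not say when to hold.

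None fills the gap.

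**Step 3: the neighbouring exception.** For thrombocytopenia the order of severity is kept. In section 3.10.2, Grade 3 reads "No bleeding: continue treatment with 25% dose reduction", while Grade 4 reads "Withhold the dose. Consider restarting with 25% dose reduction", subject to a platelet threshold and no active bleeding. Table 13 adds recovery within 14 days. Grade 4 is stricter than non-bleeding Grade 3, which is the reverse of lymphopenia.

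**Step 4: when would a scheduled result meet the gap?** From the Schedule 1 Time and Events tables (sections 7.1.1.1 and 7.1.2.1), hematology after the first dose is drawn at:

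- Cycle 1 Days 8 and 15: 2 draws, not dosing days;
- Cycle 2 Day 1: 1 draw, a dosing day;
- Day 1 of Cycles 3 to 16: 16 − 3 + 1 = 14 draws, all dosing days.

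Total = 2 + 1 + 14 = 17. On dosing days = 1 + 14 = 15. So 15 of 17 scheduled on-treatment draws fall on dosing days, and footnote 1 places assessments on those days before the drug. The end-of-treatment draw and unscheduled draws are not counted, and a subject who stops early has fewer.

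**The case against.** The best defence is that the leniency is deliberate. The Grade 4 line lifts one penalty and suggests a reduction. A hold was written for platelets and left out for lymphocytes, and lymphopenia is not a listed dose-limiting toxicity. This reading is possible, and the documents do not settle the intention. But it moves the fault to the Grade 3 row, which then holds a milder form of an event that the sponsor regards as tolerable. On either intention the two rows do not fit together and one line has to change. What stands is that the sponsor should choose the direction.

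A second defence is that the Grade 3 hold obviously carries up to Grade 4. A sensible site may read it that way, but the table does not say so. Nor does it say that a subject already held at Grade 3 who worsens to Grade 4 stays held. A reader might infer carry-up in either case; the text supports it in neither.

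Third, the consequence is limited. Table 13 is offered as guidelines. Significantly abnormal laboratory values are repeated (section 7.3.7), safety meetings take place every three weeks in Part 1 and at least monthly in Part 2 (section 12.1), and section 1.3.1 provides for following counts and infections. This stands: the subject is observed, and only the dosing action is unstated. For a subject already lymphopenic at entry, recovery to baseline also narrows the difference between the grades.

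**Conclusion.** The point holds as a minor safety-rule correction, worth considering. For possibly drug-related lymphopenia, the written rule at Grade 4 is laxer than at Grade 3, so a subject could be dosed at Grade 4 and held on improving to Grade 3, unless the 48-hour relief applied.

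The conclusion rests on reading Table 13 as written and on the absence of a lymphopenia rule elsewhere in the protocol. The 15 of 17 count shows that a scheduled first Grade 4 result after the first dose would mostly coincide with a dosing decision. It counts visits, not affected subjects. The incidence of Grade 4 lymphopenia is not given, so the number affected cannot be stated, and the protocol does not say that the result must be available before infusion.

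Stronger readings are tempting but unsupported. A reader might infer that every scheduled draw coincides with dosing, but that holds only from Cycle 2 on; the two earliest draws after first exposure, Cycle 1 Days 8 and 15, are not dosing days on Schedule 1. A reader might infer that the protocol requires dosing at Grade 4. It does not; it only fails to state a hold, and the investigator may stop treatment. A reader might also infer an effect on dose escalation or response results. Lymphopenia is not a listed dose-limiting toxicity, and nothing in the document shows an effect on the maximum tolerated dose or any endpoint.

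**What to change.** Reword the Grade 4 exception in Table 13 along these lines: *G4 lymphopenia: do not permanently discontinue; manage at least as Grade 3 (withhold to Grade 1 or baseline, including the 48-hour and >14-day Grade 3 provisions); on resumption a dose reduction of 25-50% applies as for Grade 3.* Keeping the 48-hour provision matters. Without it, a Grade 4 event that resolved quickly would have to be reduced when a Grade 3 event would not.

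If the sponsor intends no hold for lymphopenia, the alternative is to name it as an exception in the Grade 3 row, so that Grade 4 is never laxer than Grade 3.

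Either change is one line and adds no patients, visits or procedures. The first option has two costs. Dosing may be delayed, and a delay beyond 14 days brings in the section 6.3 discontinuation provision, which itself allows continuation where benefit is judged to outweigh risk. The reduction, now optional, would also become the rule outside the 48-hour relief and would use one of the two allowed per subject under section 4.4.
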